1.0 PROTOCOL SYNOPSIS

Protocol #:	SB-STR01
Title:	A Phase 1/2A Study of the Safety and Efficacy of Modified Stromal Cells (SB623) in Patients with Stable Ischemic Stroke
Study Objectives:	Primary : To evaluate the safety and tolerability of intracranial administration of SB623 cells. Safety will be determined during 2 years post-implant.
	Secondary: To evaluate clinical and radiographic response to 3 dose levels of intracranial administration of SB623 cells. The major efficacy endpoints will be determined at 6 months; measures will also be at 1, 2, 3, 4, 9, 12, and 24 months.
Background and Rationale	SB623 cells are adult bone-marrow-derived cells that have been transiently transfected with a plasmid construct encoding the intracellular domain of human Notch-1. SB623 cells secrete factors that protect neurons in models of ischemic insult. In a rat occlusion model of stroke to the middle cerebral artery region, implantation of SB623 into and around the area of the infarct resulted in improvement of neurological behavior.
	The safety of implanted SB623 cells was evaluated in a 6-month primate study and in 2 nude rat studies (4 mos. and 12 mos.). The primates were immunosuppressed with cyclosporine and the nude rats further immunosuppressed with an anti-NK cell antibody. There were no SB623-related clinical, laboratory, or histological abnormalities found.
	The stereotactic surgical delivery of cells to patients with stroke has been shown to have an acceptable safety profile in two prior clinical studies with another product. In addition, a retrospective study of over 2,650 patients undergoing stereotactic surgery during a 28-year period at one major clinic has shown a high degree of safety with the procedure.
	Finally, the European Stroke Scale (ESS), the Modified Rankin Score, the National Institute of Health Stroke Scale (NIHSS), the Fugl-Meyer scale for motor function, and a neurocognitive battery (e.g. , Rey Complex Figure Test), have been used and validated, at least for acute stroke. Fluorodeoxyglucose positron emission tomography (FDG-PET) imaging has shown that changes in metabolic activity relative to baseline in the infarct area and surrounding areas correlated with performance on the motor subscale of the ESS.
Study Design	This is an open-label safety study of stereotactic, intracranial injection of SB623 cells in patients with hemiparesis from stable ischemic stroke who have remained stable during the prior 3 weeks (based on NIHSS assessments at weeks -3 and -1). While primarily a safety study, efficacy parameters will also be evaluated. Three cohorts will receive escalating single doses of SB623, which are to be stereotactically implanted into grey or white matter sites adjacent to the infarct region. One burr-hole craniostomy will be created, and cells implanted using 3 needle tracks with 5 deposits for each track at varying depths around the damaged area. Cell

	implantation will be standardized as to volume (20 μ L/denosit) and rate (10
	implantation will be standardized as to volume ($20 \mu L/deposit$) and rate ($10 \mu L/min$), with spacing between each implant of approximately 5-6 mm. Each deposit is expected to take approximately 2-3 minutes, with each needle track being completed within 15 minutes. Each cohort will consist of 6 subjects defined by an increasing total number of cells implanted. Safety will be monitored by the Investigator, Principal Monitor, Medical Monitor, and an external Data Safety Monitoring Board. For the first cohort, a single patient will first be dosed, then evaluated over a 2 week period for safety prior to dosing the next member of the cohort. This 2- week interval will continue between each of the remaining members of this cohort. If the safety profile is acceptable for a cohort, and after review by the DSMB, the first patient in each subsequent cohort will be dosed, beginning 4 weeks after dosing of the last patient of the prior cohort. For the second and third patients in each of the subsequent cohorts, there will be an interval of 2 weeks after the prior patients prior to further enrollment.
	Safety will be monitored by clinical symptoms, laboratory findings, and MRI brain imaging. Two or more serious adverse events will trigger a review by the DSMB before continuing enrollment. Possible efficacy will be determined based on changes in the clinical measures of stroke through standardized assessments and on FDG-PET brain imaging.

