	 NIH Stroke score of >7 Two evaluations during prior 3 weeks with no more than ±1 point change in clinical evaluation using the NIH Stroke Scale Able and willing to undergo computed tomography (CT), magnetic resonance imaging (MRI), and positron-emission tomography (PET) scans of the head
	• Agree that use of antiplatelet, anti-coagulant, or non-steroidal anti- inflammatory drugs to be determined by the local medical staff and in accordance with the ACCP 2012 guideline "Perioperative Management of Antithrombotic Therapy: Antithrombotic Therapy and Prevention of Thrombosis, 9 th Edition: American College of Chest Physicians Evidence-Based Clinical Practice Guidelines", if applicable ¹ , provided that no antiplatelet, anti-coagulant, or non-steroidal anti-inflammatory drugs are to be restarted post surgery until after the Day 8 MRI is read and are determined to be safe to re-start
	 Normal emotional status; i.e., no disabling psychological deficits Ability of patient or legal authorized representative to understand and sign an Informed Consent
Exclusion	History of more than 1 symptomatic stroke
Criteria	History or presence of any other major neurological disease
	• Cerebral infarct size >100 cm ³ measured by MRI
	• Myocardial infarction within prior 6 mos.
	• Known presence of any malignancy except squamous or basal cell
	carcinoma of the skinHistory of CNS malignancy
	 History of CNS malignancy History of seizures or current use of antiepileptic medication
	 Uncontrolled systemic illness, including, but not limited to:
	hypertension (systolic >150 mm Hg or diastolic >95 mm Hg); diabetes;
	renal, hepatic, or cardiac failure
	• Uncontrolled psychiatric illness, including depression (Hamilton Score
	of > 14)
	• Total bilirubin $> 1.5 \text{ mg/dL}$
	• Serum creatinine >1.5 mg/dL

·		
	• Hemoglobin <10.0 g/dL	
	• Absolute neutrophil count $< 2000 / \text{mm}^3$	
	• Lymphocytes <800 /mm ³	
	• Platelet count $<100,000/\text{mm}^3$	
	• Liver disease supported by AST (SGOT) or ALT (SGPT) \geq 2.5 x	
	institutional upper limit of normal	
	• Serum calcium >11.5 mg/dl	
	• International Normalized Ratio of Prothrombin Time (INR) >1.2	
	• Signs and symptoms of intracranial herniation or increased intracranial	
	pressure	
	Acute intracranial hemorrhage	
	 Use of neuroleptic drugs 	
	 Unexplained abnormal preoperative test values (blood tests, 	
	electrocardiogram [ECG], chest X-ray); patients with	
	electrocardiographic evidence to suggest a recent myocardial	

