8.0 PATIENT SELECTION

8.1 Inclusion Criteria

- 1. Age 18-75 years
- 2. Documented history of completed ischemic stroke in subcortical region of MCA or lenticulostriate artery with or without cortical involvement, with correlated findings preferably by MRI or by CT if MRI is contraindicated
- 3. Between 6 and 60 months post-stroke, and having a motor neurological deficit
- 4. No significant further improvement with physical therapy/rehabilitation (confirmed by no change in NIHSS greater than ±1 within three weeks prior to enrollment)
- 5. Modified Rankin Score of 3 or 4
- 6. NIH Stroke Scale score of >7
- 7. Two evaluations during prior 3 weeks with no more than ±1 point change in clinical evaluation using the NIH Stroke Scale
- 8. Able and willing to undergo computed tomography (CT), magnetic resonance imaging (MRI), and positron-emission tomography (PET) scans of the head
- 9. Agree that use of antiplatelet, anti-coagulant, or non-steroidal anti-inflammatory drugs to be determined by the local medical staff and in accordance with the ACCP 2012 guideline "Perioperative Management of Antithrombotic Therapy: Antithrombotic Therapy and Prevention of Thrombosis, 9th Edition: American College of Chest Physicians Evidence-Based Clinical Practice Guidelines", if applicable¹, provided that no antiplatelet, anti-coagulant, or non-steroidal anti-inflammatory drugs are to be restarted after surgery until after the Day 8 MRI is read and determined to be safe to re-start
- 10. Normal emotional status; *i.e.*, no disabling psychological deficits
- 11. Ability of patient or legal authorized representative to understand and sign an Informed Consent

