9.0 INVESTIGATIONAL PLAN

9.1 Overall Study Design

This is an open-label study of stereotactic, intracranial injection of SB623 cells (SB623 cells) in patients with hemiparesis from stable ischemic stroke who have remained stable during the

prior 3 weeks (as documented by NIHSS assessments at weeks -3 and -1). Three cohorts will receive escalating singe doses of SB623, which are to be stereotactically implanted into grey or white matter sites adjacent to the infarct region. One burr-hole craniostomy will be created, and cells implanted using 3 needle tracks with 5 cell deposits for each track at varying depths. Cell implantation will be standardized as to volume (20 uL/deposit) and rate $(10 \,\mu L/min)$, with spacing between each implant of approximately 5-6 mm. Each deposit is expected to take approximately 2-3 minutes, with each needle track being completed within 15 minutes. Each cohort will consist of 6 subjects defined by an increasing total number of cells implanted. Safety will be monitored by the Investigator, Principal Monitor, Medical Monitor, and an external Data Safety Monitoring Board (DSMB). For the first cohort, a single patient will first be dosed, then evaluated over a 2 week period for safety prior to dosing the next member of this cohort. This 2-week interval will continue between each of the remaining members of the cohort. If the safety profile is acceptable for a cohort, and after review by the DSMB, the first patient in each subsequent, sequential cohort will be dosed, beginning 4 weeks after dosing of the last patient of the prior cohort. For the second and third patients in each of the subsequent cohorts, there will be an interval of 2 weeks after the prior patients prior to further enrollment.

Safety will be monitored by clinical symptoms, laboratory findings, and MRI brain imaging. Efficacy will be determined based on changes in the clinical measures of stroke and on FDG-PET brain imaging.

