10.0 STUDY ASSESSMENTS

10.1 Schedule of Study Activities

Table 4 below lists the procedures to be followed throughout the course of the study.

Confidential and Proprietary

	Scr. 1	Scr. 2	Baseline ¹	Enroll ²	Cell Admin	Follow-Up Period						Last Eval.	
Study Day			-2 to-1	-1 to 1	1	2	8						
Study Week	-3	-1	1	1	1	1	2						
Study Month								End of 1 and 2	End of 3 and 4	End of 6	End of 9	End of 12	End of 24
Informed Consent	X ³												
Demographics	Х												
Inclusion/Exclusion	Х		Х										
Medical History	Х	X^4	X ⁵	X^6									
Medication History	Х	X^4	X ⁵	X^6									
Signs & Symptoms	Х	X^4	X ⁵	X^6									
Pregnancy Test ⁷	X ⁸		X										
Physical Exam.	Х		Х									Х	Х
Vital Signs	Х	Х	Х				Х	Х	Х	Х	Х	Х	Х
Chest X-Ray and ECG	Х												
Hematology (Section 15.3)	Х	Х	Х				Х	Х	Х	Х	Х	Х	Х
Serum Chemistry (Sect. 15.3)	Х	Х	Х				Х	Х	Х	Х	Х	Х	Х
INR	Х		Х										
Occult Malig. (Sect. 10.2.2)	Х												
Lipid Panel (Section 15.3)			Х				Х	Х	Х	Х	Х	Х	Х
Cytokines (Section 15.3)			Х				Х	X (mo. 2)	X (mo. 4)	Х	Х	Х	Х
Blood for HLA antibodies	X ⁹												
Head CT					Х								
ImagingHead FDG-PET			Х							Х		Х	Х
ImagingHead MRI	X ¹⁰		Х		X ¹¹	Х	Х	X	Х	Х	Х	Х	Х

Table 4 **Study Procedures Flow Chart**

- ⁶ Only changes since Baseline
- ⁷ Only for women of childbearing potential ⁸ Serum β-HCG at Screening; serum or urine β-HCG at Baseline

¹ Only after documentation of stable stroke by two evaluations within 3 weeks prior to study entry using the NIH Stroke Scale (no more than ± 1 point)

² Enrollment only after all inclusion and exclusion criteria are verified and the patient qualifies for the study

³ Prior to any study-related procedures

⁴ Only changes since Screen 1

⁵ Only changes since Screen 2

⁹ May also be done at a pre-Screen visit

¹⁰ May instead be done at a pre-Screen visit ¹¹ Or CT overlaid with MRI from Baseline

	Scr. 1	Scr. 2	Baseline ¹	Enroll ²	Cell Admin	Follow-Up Period							Last Eval.
Study Day			-2 to-1	-1 to 1	1	2	8						
Study Week	-3	-1	1	1	1	1	2						
Study Month								End of 1	End of 3	End	End	End	End
Study Month								and 2	and 4	of 6	of 9	of 12	of 24
Clinical Stroke Evaluations	X ¹²	X ¹²	Х					X	Х	Х	Х	Х	Х
Cognitive Questionnaire			Х							Х		Х	Х
Blood for antibodies to			Х				X	\mathbf{V} (max 2)	\mathbf{V} (ma \mathbf{A})	Х	Х	X	X
SB623 and for PBMCs			Л				Λ	X (mo. 2)	X (mo. 4)	Λ	Λ	Λ	Λ
Serum Antibod. (see Sect.													
15.6 for assay schedule)													
PBMC Function (see Sect.													

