10.3.2 Enrollment (Days -1 or 1)

Enrollment can only occur after performing all assessments and verifying that the patient meets the inclusion and exclusion criteria for the study.

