5. DEFINITIONS AND DERIVED VARIABLES

Age: Age will be calculated as follows:

[Date of Informed Consent – Date of Birth] / 365.25 rounded down to the nearest integer.

Medical history: Medical history will include significant medical conditions and surgical history, medications taken within 2 weeks prior to signing the Informed Consent, and signs and symptoms occurring within 3 weeks after signing the Informed.

Concomitant medications: Concomitant medication is defined as any medication, including prescription and over-the-counter drugs taken during the 14 days prior to enrollment or used anytime during the study through 2 years post study treatment administration.

Baseline: Baseline will be defined as the last assessment available prior to first infusion of study treatment.

Change from Baseline (CFB): Change will be defined as a given post-baseline value minus the baseline value.

Dose Limiting Toxicity (DLT): A dose-limiting toxicity will be defined as any grade 3 or 4 event which is at least possibly related to study product or administration procedure.

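### The NIHSS stability check spans about two weeks, not three, and re-applying NIHSS >7 at Baseline truncates the score from which NIHSS change is measured

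*Protocol*

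**What the plan says.** **Stability.** The synopsis (Study Design) ties stability to two named visits: patients "who have remained stable during the prior 3 weeks (based on NIHSS assessments at weeks -3 and -1"). Protocol Section 9.1 repeats this ("as documented by NIHSS assessments at weeks -3 and -1"), as does SAP Section 3.1. Footnote 1 of Table 4, attached to the Baseline column, allows that visit "Only after documentation of stable stroke by two evaluations within 3 weeks prior to study entry using the NIH Stroke Scale". Inclusion 7 asks for "Two evaluations during prior 3 weeks with no more than ±1 point change in clinical evaluation using the NIH Stroke Scale" and names no visits.

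**Wider wording.** Inclusion 4 is "confirmed by no change in NIHSS greater than ±1 within three weeks prior to enrollment", again with no visits named. The synopsis (Patient Population) and SAP Section 3.2 also define stable stroke over the three weeks before enrollment. Enrollment is on Day -1 or 1, which can fall after the Baseline assessments.

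**Third score.** The full clinical stroke evaluations, including NIHSS, are done at Baseline on Day -2 to -1 (Table 4, Section 10.3.1).

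**Threshold.** The criterion is "NIH Stroke score of >7", with no visit named. Table 4 marks the inclusion/exclusion check at Scr. 1 and at Baseline. Section 10.3.2 adds: "Enrollment can only occur after performing all assessments and verifying that the patient meets the inclusion and exclusion criteria for the study".

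**Analysis.** SAP Section 5: "Baseline will be defined as the last assessment available prior to first infusion of study treatment". Change is the later value minus that value. NIHSS total and motor changes at 6 months are tested by signed-rank test at two-sided 5%, with doses pooled and no control arm (SAP 7.1.1, 7.3.2).

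**The concern.** There are two linked problems.

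First, the design claims three weeks of stability, but the visits it names test about two. The documents do not agree on whether the Baseline score counts towards the ±1 rule, so sites could apply it differently.

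Second, if NIHSS >7 is verified again on the Baseline score, patients whose Baseline rating happened to be low are turned away, while those whose rating happened to be high stay in. The retained scores lie above the patients' true level on average. Later ratings fall back towards that level, and a falling NIHSS is an improvement. With no control group to show the same drift, the test against zero credits it to treatment.

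**Working it through.** **The plan's own figures.** The plan states no power, effect size or SD for NIHSS, so there is nothing to reproduce on this point. Its only sample-size figure concerns dose-limiting toxicity: 0.6^6 = 4.67%, which agrees with the stated <5%.

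**1. Length of the window.** Scr. 1 is at week -3 and Scr. 2 at week -1 ±2 days (Section 10.2.3). The span is 21 - 7 = 14 days, or 12 to 16 with the visit window.

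**2. Why the threshold biases the reference.** Write each rating as X = T + e, rounded, where T is the patient's true score and the errors e are independent between visits with mean zero and SD s. With no true change, the expected change is

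E[X(Month 6) - X(Baseline) | selected] = -E[e(Baseline) | selected].

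- If selection uses only Scr. 1 and Scr. 2, e(Baseline) is independent of selection and the expectation is zero.
- If X(Baseline) >7 is part of selection, E[e(Baseline) | selected] is positive and the expected change is negative, a false improvement.

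**3. Size.** The inputs are assumptions: T normal with SD 3 and mean 6 to 10; s = 0.7 to 1.5; n = 18; no treatment effect. Selection is Scr. 1 >7 and Scr. 2 within ±1 of Scr. 1, with or without Baseline >7. False improvement in NIHSS total points, by simulation:

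| True mean | Error SD | >7 re-applied at Baseline | >7 on screening, single Baseline | >7 on screening, mean of three scores |
|---|---|---|---|---|
| 10 | 0.7 | 0.04 | 0.00 | 0.02 |
| 10 | 1.0 | 0.08 | 0.00 | 0.04 |
| 10 | 1.5 | 0.18 | 0.00 | 0.09 |
| 8 | 1.0 | 0.14 | 0.00 | 0.08 |
| 6 | 1.0 | about 0.2 | 0.00 | 0.13 |
| 6 | 1.5 | 0.45 | 0.00 | 0.27 |

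If the ±1 rule is also applied to the Baseline score, the range 0.04-0.45 becomes 0.03-0.31.

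**4. Effect on the test.** At n = 18, improvement is falsely declared in roughly 3-12% of trials when >7 is re-applied at Baseline. The nominal rate is 2.5%, half of the two-sided 5%. Simulation detail moves the upper end by a point or two. With the threshold on screening and the single Baseline kept, the rate stays at about 2-3%.

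**5. Would averaging three scores be better?** The error variance of change is s² + s² = 2s² with a single baseline and s² + s²/3 = (4/3)s² with a mean of three. The SD ratio is sqrt((4/3)/2) = 0.816, an 18% reduction. At s = 1 and n = 18, the standard error falls from sqrt(2/18) = 0.333 to sqrt(1.333/18) = 0.272. With selection simulated, the SD of change falls from 1.05 to 0.87, 1.43 to 1.20 and 2.07 to 1.76 at s = 0.7, 1.0 and 1.5, which is 17%, 16% and 15%. The gain is real, but the screening scores were themselves used for selection, so averaging them in brings back the 0.02-0.27 points in the last column.

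**The case against.** **The harm depends on how the text is read.** If the check at Baseline does not extend to the NIHSS score, there is no cut-off on the reference and the bias is about zero. If it does, inclusion 4 is re-applied too and the bias is smaller. This is correct, but 0.03-0.31 points remain on the second reading. The natural sense of Sections 10.3.1 and 10.3.2 is that every criterion is verified at that point.

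**The last value before treatment is a conventional baseline.** This also stands. A reference score kept out of selection is the standard protection against regression to the mean, so the definition in SAP Section 5 is not at fault. The fault lies in using the same score for eligibility.

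**The size rests on assumptions.** This stands as well. The upper end needs a true mean of 6, below the entry threshold, and noisy rating. At mean 10 and error SD 0.7-1.0 the bias is 0.04-0.08 points.

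**Stronger readings that a reader might infer.**

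- *The Baseline score is never checked.* Inclusion 4 and the definition of stable stroke cover the three weeks up to enrollment, and eligibility is verified again at Baseline. What can be said is that no passage names a comparison of that score with screening.
- *Two of the three scores are discarded.* They decide eligibility, and SAP 7.1.2 lets the latest earlier value replace a missing baseline. They are unused only in the change calculation.
- *A patient scoring 10, 10 and 13 enrolls and is credited with 3 points on returning to 10.* This requires that Baseline is not held to ±1, whereas the threshold bias requires that Baseline is re-checked. A mixed reading is conceivable, but no passage states it. Without a cut-off at Baseline, such swings occur in both directions and cancel on average.

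**Conclusion.** The concern holds in a limited form, and its severity is minor. The textual part needs no assumptions: the named stability comparison covers about 14 days and omits the Baseline NIHSS, other passages can be read to include it, and no passage says at which visit NIHSS >7 is decided.

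The statistical part is conditional on the threshold being re-applied to the Baseline score. False improvement in the NIHSS total is then about 0.04-0.45 points, with a false-improvement rate of roughly 3-12% against 2.5%. These figures assume error SD 0.7-1.5, true mean 6-10 with SD 3, and independent errors; the documents give none of these. They apply to the total score. The motor subscores share only the part of the rating error that lies in their items.

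The reach is small. NIHSS is a secondary endpoint (SAP 6.1), the primary objective is safety, and SAP 7.1.1 calls all efficacy evaluations exploratory. The ESS has only one scheduled pre-implant assessment and is not an entry criterion, so the point does not extend to it directly.

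**What to change.** 1. In inclusion 4, 6 and 7, Table 4 footnote 1 and Section 10.3, state that NIHSS >7 and the ±1 rule are decided on the Scr. 1 and Scr. 2 scores and are not re-applied to the Baseline score. The other criteria, including investigator judgement under exclusion 31, are still verified at Baseline.
2. Keep the Baseline score as the single reference in SAP Section 5.
3. Describe the stability window as the roughly two weeks tested, consistently in the synopsis (Study Design and Patient Population), Section 9.1, and SAP 3.1 and 3.2.
4. Optionally, add the mean of the three pre-implant scores as a sensitivity analysis only. It lowers the SD of change by about 15-20% but carries a small selection bias.

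Requiring the Baseline score to lie within ±1 of Scr. 1 is not a good alternative. Among patients who pass the two-visit check, it would fail about 12%, 25% and 43% at error SD 0.7, 1.0 and 1.5. It would also make the reference a selection variable again: with the threshold on screening, the bias at mean 6 and SD 1.0 rises from 0.00 to about 0.1 point.

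The cost is wording only, with no new data. The one downside is that a few patients with a Baseline score of 7 or less will be enrolled, more of them if ratings are noisy or true scores sit near the threshold.
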